### **Prior/Concomitant Therapy**

- 13 Prior exposure to MEK inhibitors.
- 14 Receipt of the last dose of systemic PN target treatment (including chemotherapy, immunotherapy, targeted therapy, biologic therapy, or monoclonal antibodies) within 4 weeks prior to the first dose of study intervention or 5 half-lives of the respective systemic PN target treatment, whichever is longer.
- 15 Has received radiotherapy in the 6 weeks prior to the start of study intervention or any prior radiotherapy directed at the target or non-target PN.
- 16 Major surgical procedure (excluding placement of vascular access) or significant traumatic injury within 4 weeks of the first dose of study intervention or an anticipated need for major surgery during the study.
- 17 Receiving herbal supplements or medications at doses known to be strong or moderate inducers of CYP3A4 unless such products can be safely discontinued at least 14 days or 5 half-lives (whichever is longer) before the first dose of study intervention (see [Appendix J](#)).
- 18 With the exception of chronic PN pain medication, receiving herbal supplements or medications at doses known to be strong or moderate inhibitors of the CYP2C19 and CYP3A4 enzymes, unless such products can be safely discontinued at least 14 days or 5 half-lives (whichever is longer) before the first dose of study intervention (see [Appendix J](#)).
- 19 Any multivitamin containing vitamin E must be stopped at least 7 days prior to initiation of study intervention.

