## 6.5 Concomitant Therapy

Any concomitant treatment, procedure, or other medication considered necessary by the investigator for the participant's safety and wellbeing, or vaccine (including over-the-counter or prescription medicines, vitamins, and/or herbal supplements) that the participant is receiving from the time of screening or receives during the study including the 30 day follow-up period following the last dose of study intervention must be recorded in the eCRF along with:

- Reason for use.
- Dates of administration including start and end dates.
- Dosage information including dose and frequency.

The AstraZeneca Medical Monitor should be contacted if there are any questions regarding concomitant or prior therapy.

If any concomitant therapy is administered due to new or unresolved AE, it should be recorded.

Participants must be instructed not to take any medications, including over-the-counter products, without first consulting with the investigator.

Strong or moderate **inducers** of **CYP3A4** are not allowed at any time during the study. During the first cycle, concomitant use of strong or moderate **inhibitors of CYP3A4 or CYP2C19**, with the exception of chronic PN medication, should be avoided until after the PK assessment. If concomitant use of selumetinib with strong or moderate CYP3A4 or CYP2C19 inhibitors is not avoidable, then the selumetinib dose should be reduced as shown in [Appendix J Table J15](#). For chronic PN pain medication fulfilling the above criteria, selumetinib should be initiated at a reduced dose as shown in [Appendix J Table J15](#). The dose of selumetinib should be reduced for the duration of concomitant therapy with the strong or moderate CYP3A4 or CYP2C19 inhibitors and for 5 half-lives afterwards. After the washout of the inhibitor is complete, the selumetinib dose can be re-escalated. The participant should be monitored closely for potential toxicities.

In vitro, selumetinib is an inhibitor of OAT3. The potential for a clinically relevant effect on the PK of concomitantly administered substrates of OAT3 cannot be excluded and they should be administered with caution.

Selumetinib capsules contain vitamin E in the form of D- $\alpha$ -tocopheryl polyethylene glycol

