1000 succinate, a water-soluble form of vitamin E which acts as a formulation excipient. The maximum daily dose of vitamin E that a study participant may receive from selumetinib is approximately 261.6 mg/day. Therefore, participants should not take any supplemental vitamin E. High doses of vitamin E have been reported to cause bleeding and interfere with blood coagulation processes. Selumetinib should be administered with caution in participants who are also receiving concomitant coumarin anticoagulant medications (eg, warfarin). These participants should have their INR monitored/anticoagulant assessments conducted more frequently and the dose of the anticoagulant should be adjusted accordingly.

Restricted, prohibited, and permitted concomitant medications/therapies are described in more detail in Appendix [J 2](#).

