## Appendix J Concomitant Medications

### J 1 Guidance Regarding Potential Interactions with Concomitant Medications

Throughout the study, participants should avoid changes to, or the addition of, all concomitant medications and, in particular, any that may affect the metabolism of selumetinib (eg, CYP2C19 or CYP3A4 moderate/strong inhibitors, as well as CYP3A4 moderate/strong inducers), unless considered clinically indicated. The use of any natural/herbal products or other “folk remedies” should be discouraged, but use of these products, as well as use of all vitamins, nutritional supplements, and all other concomitant medications must be recorded in the eCRF.

Strong or moderate **inducers** of CYP3A4 are not allowed at any time during the study. During the first cycle concomitant use of **strong or moderate inhibitors of CYP3A4 or CYP2C19**, with the exception of chronic PN pain medication, should be avoided until after the PK assessment. During the remainder of the study, if concomitant use of selumetinib with strong or moderate CYP3A4 or CYP2C19 inhibitors is not avoidable, then the selumetinib dose should be reduced as shown in [Table J15](#). For chronic PN pain medication fulfilling the above criteria, selumetinib should be initiated at a reduced dose as shown in [Table J15](#). The dose of selumetinib should be reduced for the duration of concomitant therapy with the strong or moderate CYP3A4 or CYP2C19 inhibitor and for 5 half-lives afterwards. After the washout of the inhibitor is complete, the selumetinib dose can be re-escalated. The participant should be monitored closely for potential toxicities.

In vitro, selumetinib is an inhibitor of OAT3. The potential for a clinically relevant effect on the PK of concomitantly administered substrates of OAT3 (eg, methotrexate, furosemide benzylpenicillin, baricitinib and tenofovir) cannot be excluded and they should be administered with caution.

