**Table J15 Recommended Dosage of Selumetinib for Co-administration with Strong or Moderate CYP2C19 or CYP3A4 Inhibitors**

BSA (m  )	If the current dosage is up to 25 mg/m  bid, reduce to 20 mg/m  bid		If the current dosage is up to 20 mg/m  bid, reduce to 15 mg/m  bid	
	AM	PM	AM	PM
1.10 – 1.29	25	25	25	10
1.30 – 1.49	30	25	25	20
1.50 – 1.69	35	30	25	25
1.70 – 1.89	35	35	30	25
≥ 1.90	40	40	30	30

bid, twice daily; BSA, body surface area; CYP, cytochrome P450.

Changes to, or addition of medications detailed in [Table J16](#) and [Table J17](#) should be avoided, unless clinically indicated. The lists in [Table J16](#) and [Table J17](#) are not intended to be exhaustive, and a similar restriction will apply to other agents that are known to affect CYP2C19, or CYP3A4 activity. Appropriate medical judgment is required. Please contact AstraZeneca with any queries.

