**Table J18      Restricted and Prohibited Medications/Therapies**

Prohibited medication/class of drug	Usage (including limits for duration permitted and special situations in which it is allowed)
Other systemic PN target treatment (including chemotherapy, immunotherapy, targeted therapy, biologic therapy, or monoclonal antibodies)	Not allowed for 4 weeks or 5 half-lives (whichever is longer) prior to the first dose of study intervention.  Not allowed during the study.
Radiotherapy	Not allowed for 6 weeks prior to the start of study intervention.  Radiotherapy (before or during the study) not allowed on target or non-target PNs.
Growth factors	Not allowed within the 7 days prior to screening assessment.
Blood transfusion (red blood cells or other blood products)	Not allowed within the 28 days prior to screening assessment.
Multivitamins containing vitamin E	Must be stopped 7 days prior to initiation of study intervention.  Not allowed during the study.
Herbal supplements or medications known to be strong or moderate inhibitors or inducers of CYP3A4 or strong or moderate inhibitors of CYP2C19. Substrates of OAT3.	Must be safely discontinued at least 14 days or 5 half-lives (whichever is longer) before the first dose of study intervention.  Strong or moderate inducers of CYP3A4 are not allowed at any time during the study. During the first cycle, concomitant use of strong or moderate inhibitors of CYP3A4 or CYP2C19 should be avoided until after the PK assessment. During the remainder of the study, if concomitant use of selumetinib with strong or moderate CYP3A4 or CYP2C19 inhibitors is not avoidable, then the selumetinib dose should be reduced as shown in Table J15 . The dose of selumetinib should be reduced for the duration of concomitant therapy with the strong or moderate CYP3A4 or CYP2C19 inhibitor and for 5 half-lives afterwards. After the washout of the inhibitor is complete, the selumetinib dose can be re-escalated. The participant should be monitored closely for potential toxicities.  Selumetinib may affect the plasma/serum concentrations of substrates of OAT3 and they should be given with caution.

CYP, cytochrome p450; IMP, investigational medicinal product; MEK = mitogen activated protein kinase; OAT3, organic anion transporter 3; PN, plexiform neurofibroma.

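### The sentence below Table J15 attaches a clinical-indication exception to the CYP3A4 inducers in Table J17, which the protocol elsewhere bans without condition

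*Protocol*

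**What the plan says.** The conditional wording is in Appendix J 1. Directly below Table J15 the protocol states: "Changes to, or addition of medications detailed in [Table J16](#) and [Table J17](#) should be avoided, unless clinically indicated". The following sentence says the lists are not exhaustive and that "a similar restriction will apply to other agents that are known to affect CYP2C19, or CYP3A4 activity". Table J17, as captioned in the appendix, has two columns, strong and moderate CYP3A4 inducers, and nothing else.

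The ban appears in three places. Section 6.5 states it for the whole class of inducers ("are not allowed at any time during the study. During the first cycle, concomitant use of strong or moderate") before it turns to the separate handling of the other drug class. The second paragraph of Appendix J 1 repeats the rule ("of CYP3A4 are not allowed at any time during the study. During the first cycle concomitant use of"). Table J18 in Appendix J 2 says: "Strong or moderate inducers of CYP3A4 are not allowed at any time during the study".

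Two other places bear on the point. The first paragraph of Appendix J 1 advises against changing or adding any concomitant medication. It gives CYP inhibitors as examples, "as well as CYP3A4 moderate/strong inducers), unless considered clinically indicated". Exclusion criterion 17 deals with the period ahead of dosing and applies to products "known to be strong or moderate inducers of CYP3A4 unless such products can be safely discontinued at least 14 days". A longer washout applies where five half-lives exceed that time.

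**The concern.** A rule to avoid a drug unless there is a clinical reason leaves the decision to the investigator. A rule that the drug may not be used at any point does not. The protocol applies both to the same named drugs.

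The location makes this more than a matter of style. Table J18 bans the class but names no inducer. Table J17 is the protocol's only list of named inducers, and the sentence that introduces it is the conditional one. Exclusion 17 also refers readers to Appendix J. Site staff checking whether a particular drug is an inducer are therefore likely to meet the exception.

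A site that relied on the sentence could start a banned drug, and the protocol would not tell it how to dose selumetinib. Protocol waivers are not permitted (Sections 5 and 8), so sites need a single rule.

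**Working it through.** No arithmetic applies, so the check compares the texts.

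1. **Does the conditional sentence reach inducers?** Yes. It cites Table J17, and the caption in the appendix body makes that the inducer table, with 10 strong and 15 moderate entries. The List of Tables numbers these tables one higher, so its J17 is the inhibitor table. The body captions and the in-text references agree with each other and settle the reading.

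2. **Is the ban conditional anywhere it is stated?** No. Section 6.5, the second paragraph of Appendix J 1 and Table J18 each state it without an exception.

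3. **Can the two be reconciled?** Not on the wording. Applied to a table holding only strong and moderate CYP3A4 inducers, the exception can only mean that such a drug may be changed or added when indicated. A reference to changing these drugs also presupposes ongoing use, which exclusion 17 and the ban rule out.

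4. **Where does the exception belong?** With inhibitors. Section 6.5, Appendix J 1 and Table J15 give a reduced selumetinib dose when an inhibitor cannot be avoided. Exclusion 18 exempts chronic PN pain medication from the inhibitor restriction. For inducers there is neither a dose rule nor, in exclusion 17, a pain-medication exemption. The likely origin is inhibitor wording extended to one table too many.

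5. **How far does the slip carry?** The next sentence applies a similar restriction to unlisted agents, so on its face unlisted inducers inherit the conditional rule as well.

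6. **Is any drug in both tables?** One: efavirenz is a moderate CYP2C19 inhibitor in Table J16 and a moderate CYP3A4 inducer in Table J17. A correction that only split the sentence by table would leave efavirenz both conditionally allowed and prohibited.

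**The case against.** The strongest reply is that nobody would be misled. To start an inducer on the strength of this sentence, a site would have to overlook the ban in the same subsection, in Section 6.5 and in the prohibited-medications table. Section 6.5 also says: "Restricted, prohibited, and permitted concomitant medications/therapies are described in more detail in Appendix" J 2, which holds Table J18. Participants are told to consult the investigator before taking any medication, the medical monitor is available for questions on concomitant therapy, and the text below Table J15 invites queries to the sponsor. All of this stands. It limits the consequence but does not remove the contradiction.

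A reader might count the first paragraph of Appendix J 1 as a second, equal contradiction. The documents do not support giving it that weight. It is general advice on all concomitant medications, inducers appear only in a list of examples, and the next paragraph opens with the explicit ban. It is naturally read as a general rule followed by a stricter one. Its wording is loose in the same way, but the genuine conflict is the sentence that cites Table J17.

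A reader might also infer that the protocol really permits inducers when indicated, or that exposure, PK or efficacy results could be affected. Neither follows. The ban is the repeated and dominant rule. The documents give no frequency of new inducer use and no estimate of its effect on selumetinib exposure.

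Nor should much be built on the SAP's table of disallowed concomitant medications (Section 4.1.8.2), because that section does not define disallowed. It does say that every concomitant medication is listed, so any such use would be visible.

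**Conclusion.** The inconsistency is real, and it is minor. One operative sentence in Appendix J 1 gives strong and moderate CYP3A4 inducers an exception that the rest of the protocol denies them, with no dosing instruction if the exception were used. The conclusion rests only on the wording and on taking the appendix captions as the correct table numbers. The consequence is confined to clarity of conduct. There is no numerical size to report: no sample size, alpha, estimand or analysis figure depends on it.

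**What to change.** Replace the conditional sentence and the one on unlisted agents, both below Table J15, with text to this effect:

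*Medications in Table J16 should not be changed or added unless there is a clinical indication. Medications in Table J17 are prohibited throughout the study; a medication listed in both tables (eg, efavirenz) is prohibited. The lists are not exhaustive: other strong or moderate CYP2C19 or CYP3A4 inhibitors are restricted as for Table J16, and other strong or moderate CYP3A4 inducers are prohibited as for Table J17.*

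The last part matters. If the sentence on unlisted agents stayed as it is, its reference to a similar restriction would follow two different rules and could be read as prohibiting unlisted inhibitors.

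Optionally, add to the first paragraph of Appendix J 1 that its exception does not apply to strong or moderate CYP3A4 inducers.

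The cost is a few lines of appendix text, suitable for the next amendment, with no extra data, visits or analyses.

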**Table J16      Inhibitors of CYP2C19 or CYP3A4 that AstraZeneca Recommends not to be Combined with Selumetinib**

CYP2C19	CYP3A4
Strong	Strong
Fluconazole	Indinavir
Fluvoxamine	Nelfinavir
Fluoxetine	Ritonavir
Ticlopidine	Saquinavir
Moderate	Cobicistat
(S)-omeprazole (esomeprazole) high dose 80 mg bid a	Telaprävir
stiripentol	Itraconazole
voriconazole	Ketoconazole
triclabendazole	Voriconazole
Cannabidiol b	Troleandomycin
fedratinib	Mifepristone
omeprazole	Clarithromycin
efavirenz	Lonafarnib
moclobemide	Posaconazole
	Grapefruit juice
	Conivaptan
	Tucatinib
	Ceritinib
	Nelfinavir
	Ribociclib
	Idelalisib
	Moderate
	Erythromycin
	Fluconazole
	Atazanavir
	Duvelisib
	Diltiazem

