**Table J16 Inhibitors of CYP2C19 or CYP3A4 that AstraZeneca Recommends not to be Combined with Selumetinib**

CYP2C19	CYP3A4
	Dronedarone
	Crizotinib
	Fedratinib
	Letermovir
	Aprepitant
	Lefamulin
	Imatinib
	Verapamil
	Netupitant
	Nilotinib
	Tofisopam
	Berotralstat
	Ciprofloxacin
	Voxelotor
	Isavuconazole
	Cimetidine

a There is literature evidence for esomeprazole causing weak CYP2C19 inhibition at 20 mg QD and moderate CYP2C19 inhibition at 80 mg QD, between this (eg, 20 mg bid) it is not confirmed at what dose esomeprazole changes from a weak to moderate inhibitor, therefore dose levels > 20 mg QD should be avoided with selumetinib.

b There is literature evidence for cannabidiol causing moderate CYP2C19 inhibition at doses of 750 mg bid for 7 days. There are no data at what dose cannabidiol becomes a moderate inhibitor, or if lower doses of cannabidiol cause CYP2C19 inhibition.

bid, twice daily; CYP, cytochrome P450; QD, once daily.

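### Table J16 lists esomeprazole as a moderate CYP2C19 inhibitor at 80 mg twice daily, but its own footnote puts moderate inhibition at 80 mg once daily, so it is unclear when the Table J15 selumetinib reduction applies.

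*Protocol*

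**What the plan says.** In Protocol Appendix J 1, the Moderate list in the CYP2C19 column of Table J16 contains the entry "S)-omeprazole (esomeprazole) high dose 80 mg bid", marked with footnote a. The footnote makes three statements:

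- Literature evidence shows "weak CYP2C19 inhibition at 20 mg QD and moderate CYP2C19 inhibition at 80 mg QD".
- For doses in between, "between this (eg, 20 mg bid) it is not confirmed at what dose esomeprazole changes from a weak to moderate inhibitor".
- The resulting instruction is "therefore dose levels > 20 mg QD should be avoided with selumetinib".

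The table's key settles the notation: "bid, twice daily; CYP, cytochrome P450; QD, once daily". The text under Table J15 says that changing or adding drugs listed in Tables J16 and J17 "should be avoided, unless clinically indicated".

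Three other rules use the inhibitor class:

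- Exclusion criterion 18 covers products taken at doses known to inhibit CYP2C19 or CYP3A4 strongly or moderately, unless they can be stopped in time before the first dose. Chronic PN pain medication is exempt.
- Section 6.5 and Appendix J 1 ask that such inhibitors be avoided in the first cycle until the PK assessment is done.
- The same two places require the reduced selumetinib dose of Table J15 where use of a strong or moderate inhibitor cannot be avoided.

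**The concern.** The row and its footnote attach the moderate class to different daily doses of the same drug. The footnote does not mention 80 mg twice daily, so it does not explain the figure in the row. It gives another one.

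This is more than background pharmacology. Exclusion criterion 18 turns on dose, and Table J16 with its footnote is where the protocol supplies a dose for esomeprazole. The Table J15 reduction depends on whether the inhibitor is at least moderate, and it runs for as long as the inhibitor is taken plus a washout. If two investigators read the entry differently, they could reach different selumetinib doses for participants with the same co-medication. A moderate inhibitor missed before the PK day could also affect the Cycle 1 exposure parameters, which serve a secondary objective.

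**Working it through.** The plan states no derived figure on this point, so there is nothing to reproduce first. The check has three steps.

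**Step 1: daily esomeprazole dose = unit dose × doses per day.**

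- Table J16 row: 80 mg × 2 = 160 mg/day.
- Footnote a, moderate evidence: 80 mg × 1 = 80 mg/day.
- Footnote a, weak evidence and avoidance level: 20 mg × 1 = 20 mg/day, with avoidance above it.
- Footnote a, example of an unconfirmed dose: 20 mg × 2 = 40 mg/day.

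Row against the footnote's moderate evidence: 160 / 80 = 2-fold. This is the like-for-like comparison, since both figures describe the moderate class.

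**Step 2: what each text implies by dose range.** This takes inhibition not to weaken as the dose rises.

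| Esomeprazole, mg/day | Row | Footnote a | Does Table J15 apply if use is unavoidable? |
|---|---|---|---|
| up to 20 | not named | weak at 20 | no conflict |
| above 20, below 80 | not named | avoid; class unconfirmed | unclear |
| 80 to below 160 | not named | moderate | row and footnote disagree |
| 160 and above | moderate | moderate | no conflict |

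**Step 3: size of the selumetinib difference.** Total daily doses (AM + PM) come from Table 6 (starting dose) and the first dose columns of Table J15 (reduction to 20 mg/m² bid). Reduction = (Table 6 − Table J15) / Table 6.

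| BSA, m² | Table 6, mg/day | Table J15, mg/day | Reduction |
|---|---|---|---|
| 1.1 to 1.29 | 30 + 30 = 60 | 25 + 25 = 50 | 10/60 = 16.7% |
| 1.3 to 1.49 | 35 + 35 = 70 | 30 + 25 = 55 | 15/70 = 21.4% |
| 1.5 to 1.69 | 40 + 40 = 80 | 35 + 30 = 65 | 15/80 = 18.8% |
| 1.7 to 1.89 | 45 + 45 = 90 | 35 + 35 = 70 | 20/90 = 22.2% |
| 1.90 and above | 50 + 50 = 100 | 40 + 40 = 80 | 20/100 = 20.0% |

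Where the two readings part, the total daily selumetinib dose differs by 17-22%.

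**The case against.** The best defence is that the footnote belongs to the row, and that anyone who reads the whole entry finds one clear instruction: avoid anything above 20 mg once daily. That level covers 80 mg once daily and 80 mg twice daily alike, so for avoidance the statements nest and do not compete. The row can also be read as naming one high dose without saying that lower doses are not moderate. The lists are described as not exhaustive, medical judgment is asked for, and queries go to the sponsor. Finally, Section 4.3 reports a flat dose-exposure-response relationship from 20 to 30 mg/m² bid, and the first Table J15 step is to 20 mg/m² bid.

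Much of this stands. A reader might infer three thresholds that cannot all hold, an 8-fold spread (160 / 20), and a participant on 40 mg once daily whom the row leaves free and the footnote restricts. The documents do not support that. The 20 mg figure is a precautionary avoidance level, set below the dose at which the footnote cites moderate inhibition. It is compatible with that evidence, and it applies to the participant on 40 mg once daily. Nor can a dose difference of about a fifth be claimed for everyone between 20 and 160 mg/day. Table J15 applies only to a strong or moderate inhibitor whose use is unavoidable, and below 80 mg/day the footnote does not assign that class.

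What the defence does not remove is the mismatch between twice daily in the row and once daily in the footnote for the same 80 mg. An avoidance instruction does not settle what happens when use cannot be avoided, which is the case Table J15 exists for. A drug listed with a dose is also not helped by the list being open-ended. The flat relationship in Section 4.3 does not cover exposure in the presence of an inhibitor.

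**Conclusion.** The inconsistency is real and narrow. The row and footnote a differ 2-fold on the daily dose at which esomeprazole counts as a moderate CYP2C19 inhibitor. The practical conflict falls on participants taking 80 to under 160 mg/day whose use is not avoidable; for them the total daily selumetinib dose is either the Table 6 starting dose or 17-22% below it. Above 20 and below 80 mg/day there is a gap and not a contradiction: use is to be avoided, but the class is unconfirmed, so a different selumetinib dose is possible and not established.

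This rests on reading the dose in the row as the condition for the moderate label, on inhibition not weakening with dose, and on a participant at the Table 6 starting dose. Someone already on a lower dosage would use the second pair of columns in Table J15. The documents do not say how many participants take esomeprazole at these doses, so the effect on the trial cannot be sized. No efficacy estimand, power figure or significance level depends on it. It is still worth correcting, because it bears on when a dose of study drug changes.

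**What to change.** The sponsor should reconcile the esomeprazole row of Table J16 with footnote a so that both give the same dose and frequency for the moderate class. Appendix J should then state two things separately: the esomeprazole dose that counts as moderate for exclusion criterion 18, the first-cycle rule in Section 6.5 and the Table J15 reduction; and the level above which the drug is to be avoided. It should also say how Table J15 is to be handled for doses above the avoidance level whose class is unconfirmed. The values are for the sponsor to set, and none is proposed here.

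The cost is a correction of about a line to one row and its footnote, plus a clarifying sentence. No assessment, analysis or sample-size change follows.
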